## STATEMENT OF COMPLIANCE

The trial will be carried out in accordance with International Council on Harmonisation Good Clinical Practice (ICH GCP) and the following:

- United States (US) Code of Federal Regulations (CFR) applicable to clinical studies (45 CFR Part 46, 21 CFR Part 50, 21 CFR Part 56, 21 CFR Part 312, and/or 21 CFR Part 812).

National Institutes of Health (NIH)-funded investigators and clinical trial site staff who are responsible for the conduct, management, or oversight of NIH-funded clinical trials have completed Human Subjects Protection and ICH GCP Training.

The protocol, informed consent form(s), recruitment materials, and all participant materials will be submitted to the IRB for review and approval. Approval of both the protocol and the consent form(s) must be obtained before any participant is consented. Any amendment to the protocol will require review and approval by the IRB before the changes are implemented to the study. All changes to the consent form(s) will be IRB approved; a determination will be made regarding whether a new consent needs to be obtained from participants who provided consent, using a previously approved consent form.

## 1 PROTOCOL SUMMARY

### 1.1 SYNOPSIS

Title:	Brain Mechanisms of Reducing Polysubstance Use Following a Novel Body-mind Intervention
Grant Number:	R61AT010138
Study Description:	
The R61 phase of the study aims to understand the mechanisms and training effects of evidence-based body-mind training on self-control in polysubstance use. Specifically, it aims to understand brain mechanisms of improved self-control following an evidence-based preventive intervention - integrative body-mind training (IBMT).

Objectives:	
Primary Objective: This study aims to examine brain mechanisms of improved self-control following IBMT.

Endpoints:	
Primary Endpoint: Brain outcome

Study Population:	
70 adults (both sexes) who are at least 18 years old with polysubstance use in the Lubbock, TX.

Phase or Stage:	
N/A

Description of Sites/Facilities Enrolling Participants:	
The participating site/facility is Texas Tech University, where enrollment of participants happens. There is no foreign site.

Description of Study Intervention/Experimental Manipulation:	
Experimental manipulation is evidence-based preventive intervention - integrative body-mind training (IBMT) and will be offered as a group for 10 sessions across 4 weeks.

Study Duration:	
12 months

Participant Duration:	
3 months

### 1.2 SCHEMA

**Figure 1. Flowchart of screening, inclusion, and assessment process**

### 1.3 SCHEDULE OF ACTIVITIES

	Pre-screening	Visit 1 Day 1	Visit 2 to Visit 11 Day 3 ±1 to Day 30±1	Visit 12 Day 31 ±2	Visit 13 Day 90 ±2
Review Eligibility	X				
Informed Consent		X			
Demographics		X			
Outcome Evaluation					
Brain Assessment (MRI scan)		X		X	X
Cognitive Assessment (Self-control tasks)		X		X	X
Randomization		X			
Control & Experimental Interventions		X	X		
Adverse Events Reporting		X	X	X	X

## 2 INTRODUCTION

### 2.1 STUDY RATIONALE

Polysubstance use ties with numerous consequences for adults, including poor performance, impaired driving, injuries, risky behaviors (e.g., unsafe sex), increased risk for substance use disorders (SUDs), and heightened risk for morbidity and mortality. Treatment outcomes, however, are far from optimal since treatments often fail to capitalize on important target domains linked to addiction outcomes. We propose to address this urgent and critical public health issue by examining the effectiveness of a brief evidence-based mindfulness intervention – Integrative Body-Mind Training (IBMT) in adults with polysubstance use through randomized clinical trials (RCTs). We will examine if the intervention can improve brain function and structure in self-control related regions and networks, thereby reducing polysubstance use. Outcomes from this study will inform prevention and treatment option to promote health and well-being for individuals with polysubstance use.

### 2.2 BACKGROUND

Tobacco use is the leading cause of cancer and the leading preventable cause of death. Alcohol use is responsible for ~88,000 deaths each year in the U.S. and is another primary preventable cause of cancer. The combined use of cigarettes and alcohol is associated with an increased risk of mortality and morbidity. Previous research shows that one target domain (mechanism) for polysubstance use involves deficits in self-control networks including the prefrontal cortex (PFC), the anterior cingulate cortex (ACC), and the ACC-Striatum circuit. Deficits in self-control have been linked to SUDs, and can be ameliorated through interventions. Mind Body Interventions such as mindfulness meditation (MM) have shown to decrease substance use and have the potential to minimize negative outcomes resulting from deficits in self-control. Although research suggest MM is efficacious at reducing problematic use, some studies are replete with limitations including the lack of: adequate control conditions, effective mindfulness programs, and assessments for biomarkers of change. As a result, the support for MM has been less robust in some work, thereby warranting more rigorous randomized controlled trials using appropriate MM program and active control, as well as standardized and theoretically driven assessments. Self-control/EF and attention deficits can be improved through brief intervention. Our preliminary RCTs in healthy adults provide support for our clinical trial by showing improvement in self-control/EF, attention, cognitive functioning, emotion, stress reduction, and quality of life following brief IBMT intervention, suggesting its potential effectiveness in adults with polysubstance use.

### 2.3 RISK/BENEFIT ASSESSMENT

#### 2.3.1 KNOWN POTENTIAL RISKS

*The study includes behavioral, cognitive, and brain assessments, as well as mindfulness-based intervention.*

##### *Behavioral and Cognitive Assessments*

- *Immediate risks: Potential boredom from completing the questionnaires and interviews.*
- *Long-term risks: Data including self-report, questionnaires and interview involve risk of breaches in confidentiality.*

- *Alternative procedures: There are no other available alternative procedures to assess behavior and cognition, since to assess the behavior and cognition, we have to use the actual assessments. To minimize immediate risks, breaks in between questionnaires and interviews are offered to reduce boredom. To minimize long-term risks, all information about the specific individuals will be maintained as confidential. Absolutely no names of subjects are used in published reports or in presentations in scientific meetings. All data will be kept in locked files and digital media in the PI's laboratory. Reference to individual subject data will be made with a number and letter code for each subject. Any risks to participants are minimal and are outweighed by the benefits of increasing our scientific understanding of improving self-control and reducing polysubstance use.*

#### *Brain Assessments*

- *Immediate risks: Potential boredom from completing the MRI scan, the possibility of becoming uncomfortable in the enclosed space of the scanner.*
- *Long-term risks: MRI data involves risk of breaches in confidentiality.*
- *Alternative procedures: There are no other available alternative procedures to brain, since to assess the brain, we have to use the actual MRI assessments.*

#### *Mindfulness-based Intervention*

- *Immediate risks: Potential boredom from completing the intervention.*
- *Long-term risks: No known risk based on our previous studies.*
- *Alternative procedures: There are no other available alternative procedures, since the goal is to test the effects of the mindfulness-based intervention. To minimize immediate risks, breaks during the session are offered to reduce boredom.*

---

### 2.3.2 KNOWN POTENTIAL BENEFITS

#### *Immediate potential benefits*

*The immediate potential benefits from participant in this study include that participants generally find the experimental paradigms enjoyable (i.e. meditation and relaxation state) during the intervention sessions.*

#### *Long-term potential benefits*

*The long-term potential benefits include that participants have the opportunity to learn more about approaches and methods of improving self-control during the intervention and may be able to apply the learned knowledge in their everyday life and reduce polysubstance use.*

---

### 2.3.3 ASSESSMENT OF POTENTIAL RISKS AND BENEFITS

*Because this is a study that examines the effects of an intervention on behavior, cognition, and behavior, it is inevitable to expose participants to risk of boredom during their assessments and interventions, as these assessments and intervention are necessary for us to evaluate the effects of the intervention.*

*To minimize immediate risks of potential boredom from completing the behavioral and cognitive assessments, brain assessments, and mindfulness-based intervention, breaks during the assessments and interventions are offered to reduce boredom and give participants time to rest. To minimize long-term risks, all information about the specific individuals will be maintained as confidential. Absolutely no names of subjects are used in published reports or in presentations in scientific meetings. All data will be kept in*

*locked files and digital media in the PI's laboratory. Reference to individual subject data will be made with a number and letter code for each subject.*

*Based on the risks of boredom and breach in confidentiality, as well as our approaches to minimize these risks, we conclude that any risks to participants are minimal and are outweighed by the benefits of increasing our scientific understanding of improving self-control in adults with polysubstance use, as well as the benefits of potentially having the participants learning ways to improve self-control and potentially reduce polysubstance use in their everyday life.*

### 3 OBJECTIVES AND ENDPOINTS

OBJECTIVES	ENDPOINTS	JUSTIFICATION FOR ENDPOINTS
Primary		
This study aims to investigate the modulation effects of a novel body-mind intervention on brain outcomes.	Baseline and post-intervention assessments of brain outcomes (functional activity in anterior cingulate cortex/medial prefrontal cortex).	The novel body-mind intervention should lead to improvement in brain outcomes at post-intervention compared to baseline.
Secondary		
N/A	N/A	N/A
Tertiary/Exploratory		
N/A	N/A	N/A

### 4 STUDY DESIGN

#### 4.1 OVERALL DESIGN

*The study is a randomized control trial (RCT) involving two groups – IBMT (Arm 1: experimental manipulation) and RT (Arm 2: control group) group. Participants in each group will be assessed at baseline and post-intervention using behavioral and brain assessments as described in Section 1.3. Automatic randomization will be conducted by study staff and used to assign participants to each arm/group condition using an algorithm before the baseline assessment. This randomization procedure ensures balance between groups on gender while also balancing total treatment numbers.*

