#### 5.4 SCREEN FAILURES

Screen failures are defined as participants who consent to participate in this study but are not subsequently assigned to the study intervention or entered in the study. Individuals who do not meet the criteria for participation in this trial (screen failure) because of meeting one or more exclusion criteria that are likely to change over time may be rescreened. Examples include the successful removal of metal

devices that previously made them ineligible for an MRI scan. Rescreened participants will be assigned the same participant number as for the initial screening.

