### 6.3 MEASURES TO MINIMIZE BIAS: RANDOMIZATION AND BLINDING

*To minimize potential biases, participants are randomized based on automatic covariate conducted by Co-I using an adaptive algorithm. Participants are blinded to the intervention. Specifically, they were told that they will be engaged in body-mind intervention, without knowing whether or not the intervention they received is the experimental manipulation or control intervention. See methods of analysis in **Section 9, Statistical Considerations** for details on randomization. Additionally, research staff who assesses participants are also blinded of the participants' intervention condition. Randomization code is maintained by the Co-I. A planned breaking of randomization code and blinding would occur for any participants who reported serious adverse events. The PI and Co-I will identify which group the participant is in, without the need for research staff to be involved in knowing the participant's intervention group.*

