### 7.2 PARTICIPANT DISCONTINUATION/WITHDRAWAL FROM THE STUDY

Participants are free to withdraw from participation in the study at any time upon request.

An investigator may discontinue a participant from the study for the following reasons:

- Significant study intervention non-compliance, unless varying compliance is an aspect of the study objectives
- Lost-to-follow up; unable to contact subject (see **Section 7.3, Lost to Follow-Up**)
- Any event or medical condition or situation occurs such that continued collection of follow-up study data would not be in the best interest of the participant or might require an additional treatment that would confound the interpretation of the study
- The participant meets an exclusion criterion (either newly developed or not previously recognized) that precludes further study participation

The reason for participant discontinuation or withdrawal from the study will be recorded. Subjects who sign the informed consent form and are randomized but do not receive the study intervention may be replaced. Subjects who sign the informed consent form, and are randomized and receive the study intervention, and subsequently withdraw, or are discontinued from the study, will not be replaced.

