## 8 STUDY ASSESSMENTS AND PROCEDURES

### 8.1 ENDPOINT AND OTHER NON-SAFETY ASSESSMENTS

*The study involves assessing participants at baseline, post-intervention, and one-month follow-up. The participant will be screened for eligibility after consenting. They will fill out demographic questionnaires and MRI screening form to determine their eligibility. Next, they will undergo behavioral and brain assessments by trained research staff and/or MRI technician. All non-brain assessments will be conducted at PI's lab for all participants to decrease variability. All brain assessments will be conducted at Barrow Neurological Institute for all participants to decrease variability.*

*Below is a list and description of the assessments:*

- **Imaging assessments**  
*MRI Scan – provides images of brain structure and function*
- **Administration of questionnaires, interviews**  
*Behavioral assessments – demographic questionnaire, subjective reports of polysubstance use*

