### 9.4.2 ANALYSIS OF THE PRIMARY ENDPOINT(S)

*The primary endpoints are brain assessments and are all repeated measures assessed at baseline and post-intervention. For brain assessment of brain assessment of functional activity, whole-brain analyses of fMRI timeseries during resting state will be calculated and for all endpoints based on standardized processing pipelines of fMRI data using REST software ([www.restfmri.net](http://www.restfmri.net)). After these data preprocessing and calculation, numerical values will be generated for each brain voxel. Next, the effects of intervention (IBMT vs. RT) on primary endpoints will be examined using repeated-measures ANOVA with time x group interaction effect. Threshold-free cluster enhancement approach will be used to identify clusters showing significant effects. Variance and covariance across repeated measures will be calculated as part of the ANOVA. Age and sex will be included as covariates to control for potential confounding effects of age and sex on brain outcomes. Results will be presented as F values for the interaction effect, along with p values to indicate statistical significance. Normality and homogeneity of variance assumptions will be checked using SPSS built-in tools for ANOVA. Multiple comparison corrections will be conducted using FDR correction. Missing data will be handled with case-wise deletion.*

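### Arms are assigned before the baseline scan, so baseline is measured after allocation and a failed baseline scan becomes an avoidable post-randomisation exclusion

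*Combined protocol and SAP*

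**What the plan says.** - **Section 4.1, Overall Design.** Study staff conduct the randomisation, which is "used to assign participants to each arm/group condition using an algorithm before the baseline assessment". The procedure is meant to balance gender and total numbers between arms.
- **Section 1.3, Schedule of Activities.** The eligibility row ("Review Eligibility X") is marked at pre-screening. The randomisation row ("Randomization X") is marked at Visit 1, Day 1. Consent, the baseline MRI, the self-control tasks and the first intervention session are also marked there. No order within the visit is given.
- **Section 8.1, Endpoint and Other Non-Safety Assessments.** Screening follows consent: "They will fill out demographic questionnaires and MRI screening form to determine their eligibility". The behavioural and brain assessments come next. Randomisation is not placed in this sequence.
- **Section 5.4, Screen Failures.** These are "participants who consent to participate in this study but are not subsequently assigned to the study intervention" or do not enter the study. The example is metal that rules out an MRI.
- **Section 6.3, Randomization and Blinding.** Participants are "randomized based on automatic covariate conducted by Co-I using an adaptive algorithm". The Co-I keeps the code, and staff who assess participants are to be blind to arm.
- **Section 7.2, Participant Discontinuation/Withdrawal.** Consented people who are "randomized but do not receive the study intervention may be replaced".
- **Section 9.3, Populations for Analyses.** The analysis set needs all ten sessions and complete primary-endpoint data.
- **Section 9.4.2, Analysis of the Primary Endpoint(s).** "Missing data will be handled with case-wise deletion".

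**The concern.** The primary test is the time-by-group interaction on resting-state fMRI, so the baseline scan supplies half of the contrast. A baseline taken before allocation cannot be affected by the arm. A baseline taken afterwards is protected only by blinding.

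The order also decides what a failed baseline scan means. Before allocation, it is a screening loss and leaves the randomised set untouched. After allocation, it removes someone whom the algorithm has already counted, which can disturb the balance on gender and numbers that Section 4.1 seeks. Replacement restores the count but not the set of people who were randomised, and Section 7.2 does not say how a replacement is allocated.

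Such failures are foreseeable. Section 2.3.1 lists discomfort in the enclosed scanner as a risk.

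**Working it through.** **1. Following one participant through the text.** Take someone who consents, passes the MRI screening form and then cannot complete the baseline scan.

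- By Section 4.1 this person already has an arm.
- By Section 9.3 the person is outside the analysis set, because the primary data are incomplete. Section 9.4.2 deletes the case in any event.
- By Section 7.2 the person may be replaced if no session was received.
- If randomisation followed the scan, the same person would be a screen failure as Section 5.4 defines it.

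Nothing elsewhere changes this. Section 6.3 refers to Section 9 for details of randomisation, and Section 9 contains none.

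**2. The plan's own power figure.** Section 9.2 gives d = 0.80, 35 per group and 90% power. Alpha and sidedness are not stated for that calculation, so I assume 5% two-sided. For a two-sample t-test with n per arm, the noncentrality is d × √(n/2) on 2(n − 1) degrees of freedom.

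- n = 35: 0.80 × √17.5 = 3.35, power 91.0% (normal approximation 91.7%). The stated 90% reproduces, with no losses.
- n = 28, from the 56 completers in Section 5.5: 0.80 × √14 = 2.99, power 83.6% (normal approximation 84.9%).

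**3. If baseline scan failures came on top of the planned attrition.** Let x be the share of the 70 lost at the baseline scan. The documents give no value, so the range is an assumption. Number analysed = 70 × (1 − x) × 0.80.

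| x (assumed) | Lost at scan | Analysed | Power (t-test) |
|---|---|---|---|
| 0% | 0 | 56.0 | 83.6% |
| 3% | 2.1 | 54.3 | 82.5% |
| 5% | 3.5 | 53.2 | 81.7% |
| 10% | 7.0 | 50.4 | 79.5% |
| 15% | 10.5 | 47.6 | 77.1% |

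**4. Why this table is an upper bound.**

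- Section 4.4 counts a participant as a completer only if the baseline assessment was done. A failed baseline scan therefore fits naturally among the 70 − 56 = 14 non-completers already allowed for. If it is counted there, the extra loss is nil.
- If those lost are replaced under Section 7.2, the numbers are restored.
- With recruitment held at 70, reordering alone gives 70 × (1 − x) randomised and the same number analysed. Power is recovered only if more people are recruited. To randomise 70 takes 70/(1 − x): 70/0.95 = 73.7, so 74 people at 5%; 70/0.90 = 77.8, so 78 people at 10%.

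**The case against.** **A stronger reading that the text does not support.** A reader might infer that randomisation also precedes MRI eligibility screening, so that people with MRI contraindications are randomised. No section says so, and three point the other way. Section 5.4 treats MRI-incompatible metal as a screen failure in someone not assigned. Section 8.1 puts the MRI form before the assessments. Section 1.3 puts eligibility review at pre-screening. Section 4.1 is compatible with screening, then randomisation, then the scan. What stands is that the order is unstated, and that Sections 1.3 and 8.1 disagree on whether eligibility review comes before or after consent.

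**Bias may be small.** Section 6.3 blinds participants and assessors, and Section 9.4.2 uses a standardised processing pipeline. Under that blinding, a scan failure before treatment has no evident route to depend on arm. This largely stands. It relies, however, on the assessors being kept apart from allocation and on the scan preceding the first session. Section 4.1 has study staff randomise, and Section 1.3 does not order the scan and the session.

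**Study staff and Co-I need not conflict.** A Co-I can be counted as study staff, so this is an ambiguity rather than a proven contradiction. One sentence would settle it.

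**Reordering makes nobody scannable.** This is correct, and it is why the case does not rest on power.

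**Conclusion.** The point holds as a cheap improvement. Section 4.1 states the order, and no other section cures it: the baseline MRI and tasks follow allocation, and people who cannot complete the baseline scan become exclusions from the randomised set that a different order would avoid.

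The effect on power is small and cannot be derived from the documents. At an assumed 5–10% on top of planned attrition it is about 2 to 4 percentage points (83.6% to 81.7–79.5%, d = 0.80, two-sided 5% assumed). It is nil if these losses lie within the 20% or are replaced.

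A reader might also infer that the baseline values will be biased. The documents do not show that. They show a baseline protected by blinding alone, where the order of events could protect it as well.

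**What to change.** - **Sections 4.1 and 1.3.** Give the Visit 1 order explicitly: consent, confirmed eligibility including the MRI screening form, completed baseline MRI, baseline tasks, randomisation, first intervention session.
- **Sections 1.3, 5.4 and 8.1.** Align them with that order. Say which eligibility checks are made at pre-screening and which after consent.
- **Sections 4.1 and 6.3.** State that only the Co-I who holds the code runs the algorithm, and that assessing staff do not. Put the randomisation details in Section 9, where Section 6.3 sends the reader.

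**Cost.** The change is to wording and to the order of events, with no new assessment. A few more people may have to be consented and scanned to reach 70 randomised (about 4 to 8 at the assumed 5–10%). Randomisation must fit between the scan and the first session, although Section 8.1 uses separate places for scanning and other assessments and Section 6.1.2 delivers sessions in groups. The condition should be a completed scan. The documents describe no same-day image review, so an image found unusable later would remain a post-randomisation loss.
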